The analysis will be conducted using an analysis by intention to treat (ITT) and will include all available data, maintaining participants as members of their allocated group. The primary analysis will likely be a linear regression model adjusted for baseline stratification covariates (above/below the median FSM6) and the baseline value of the outcome. As there is variation in business as usual (BAU) across sites, a multi-level model will be applied, allowing for pupils to be nested within schools. Individual outcomes will be incorporated into the model with an inverse propensity weight for each participant.

Secondary outcomes will be assessed similarly by establishing diagnostic plots to identify the most appropriate regression approach, including stratification factors and baseline covariates within a multi-level model.

As the generation of intervention and comparison groups occurs after the final follow-up, we do not account for missing data.

We will not conduct any Complier Average Causal Effects (CACE) analysis for this strand of the study. The nature of the targeted support for this sub-group presents significant challenges in measuring compliance, such as the whole school intervention. This targeted intervention is highly personalised and adaptable to the individual needs of each student, which means that the intensity and frequency of engagement can vary greatly.

Sub-group analysis will be conducted to estimate how the treatment effects vary within groups. This means estimating heterogeneous effects, namely, conditional average treatment effects (CATE). The groups consist of sex, ethnicity and FSM. After passing the balancing test and robustness checks, the approach will achieve a matched sample, thus obtaining the average treatment effect. Then, we will condition the ATE on the respective group variables to obtain treatment effect by stratum, namely the CATE.

16. Appendix 3: Engagement tool

Delivery Element and Engagement Standard	Engagement Scoring	TOTAL POINTS: 100
Individual Training		

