The propensity score is the probability of receiving the intervention conditional on measured participant covariates. It is, in essence, a balancing score. If we have two populations, the intervention and control populations, both of which have a similar propensity score, the distribution of baseline covariates will be the same in the intervention and control groups. Hence, we can remove confounding effects by comparing participants who share a propensity score. This is analogous to that induced by randomisation in RCTs.

For the propensity score, the covariates for the matching will be socio-demographic variables such as sex, age, ethnicity, FSM, attendance, exclusions, suspensions and pre-test outcomes for the primary and secondary outcomes. As is often the case in PSM, the selection of the variables will depend on which model delivers the best balance in the matched sample.

A counterfactual control group will be derived using PSM to draw causal inferences of the relative effect of the intervention. A probit regression model will be employed. Callipers of width 0.2 of the standard deviation of the width of the logit propensity score will be employed to maximise matching. Once the propensity scores have been generated, they will be incorporated into the primary and secondary analysis using inverse propensity score weights (IPSW), because this will reduce the sample size required for the control group. One potential limitation of weighting approaches, akin to Horvitz-Thompson's estimation, is the potential for a substantial increase in variance when dealing with extreme weights (i.e. when estimated propensity scores approach 0 or 1). This increased variance is justified if the model is

appropriately specified and the weights are accurate. However, a concern arises when some extreme weights are more closely linked to the estimation process rather than the true underlying probabilities. To mitigate the impact of extreme weights, we would consider weight trimming as a solution, whereby weights exceeding a certain maximum value are capped at that maximum (Stuart, 2010). Robustness check through other matching techniques will allow us to test the sensitivity of this approach to increase in variance. Other matching approaches will include exact matching, Nearest-Neighbour matching, Mahalanobis distance, PSM with different calliper widths, and CEM, as discussed further in section 3.4.3 below.

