The success of matching in reducing the imbalance of covariates will be reported by displaying the imbalance before and after matching, that is, between the unmatched and matched samples. The reduction of imbalance will be measured through the reduction in mean and median standardised bias and Rubin's B and Rubin's R. As discussed in Caliendo and Kopeinig (2008), a reduction to a standardised bias between below 2% to 5% is a good sign. Regarding Rubin's metrics, we will consider $B < 25$ and R between 0.5 and 2 enough balance (Rubin, 2001).

Finally, as acknowledged in the literature, the main limitation of all matching approaches is the inability to control for unobservable covariates (Abadie & Imbens, 2006; Morgan & Winship, 2015). While we have carefully controlled for observable factors through the matching process, there may be unobserved variables, such as student motivation or parental involvement, that could influence the outcome. However, by employing a rigorous matching strategy and drawing from a comprehensive set of observed covariates, we aim to mitigate the potential impact of unobservable confounders as much as possible.

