3.4.5 Subgroup analyses

Sub-group analysis will be conducted to estimate how the treatment effects vary within groups. This means estimating heterogeneous effects, namely, conditional average treatment effects (CATE). The groups consist of sex, ethnicity and FSM. We will aim to minimise the number of strata within each category whenever applicable and necessary. For example, ethnicity will be divided into minority and non-minority to maximise statistical power.

After passing the balancing test and robustness checks, the approach will first achieve a matched sample, thus obtaining the average treatment effect on the treated (ATET). Then, we will condition the ATET on the respective group variables to obtain treatment effect by stratum, namely the CATE.

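### QED sub-group effects come from a sample matched and balance-checked only overall, so false sub-group differences can arise if selection for support differs by group

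*Protocol*

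**What the plan says.** Protocol Appendix 2 defines the sub-groups: "The groups consist of sex, ethnicity and FSM". It then sets an order of work. First: "After passing the balancing test and robustness checks, the approach will achieve a matched sample, thus obtaining the average treatment effect". Next: "Then, we will condition the ATE on the respective group variables to obtain treatment effect by stratum, namely the CATE". SAP 3.4.5 keeps that order with a different estimand: "Then, we will condition the ATET on the respective group variables to obtain treatment effect by stratum, namely the CATE". It adds that "ethnicity will be divided into minority and non-minority to maximise statistical power". The ATE and the ATET need reconciling, but the point below is the same for either.

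On the propensity score, SAP 3.3 says that "the covariates for the matching will be socio-demographic variables such as sex, age, ethnicity, FSM, attendance, exclusions, suspensions and pre-test outcomes". No interaction between a group variable and another covariate is named. Variables are chosen by overall performance: "the selection of the variables will depend on which model delivers the best balance in the matched sample". Balance is reported by "displaying the imbalance before and after matching, that is, between the unmatched and matched samples", using standardised bias and Rubin's B and R. The tests in SAP 3.4.3 also compare the two whole groups. Neither document plans a balance check, a score or a match within a sub-group.

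The QED outcome model is a multilevel regression with inverse propensity weights, adjusted for the FSM stratifier and the baseline value of the outcome (Protocol Appendix 2, SAP 3.4.1). The sub-group paragraphs do not say whether that model is used for the CATEs.

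**The concern.** A propensity score fitted with main effects balances each covariate across the pooled sample. It need not balance that covariate among boys and girls separately. Suppose boys are selected for support mainly on externalising problems and girls mainly on emotional ones. A common slope then under-corrects externalising in boys and over-corrects it in girls. The two errors cancel in the pooled check and reappear with opposite signs after the split.

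How selection works is not fixed in advance. Protocol Appendix 2 and SAP 3.3 give the absence of set eligibility parameters as the reason why comparable control pupils cannot be identified directly, and Appendix 2 has diploma staff identifying the pupils. Nothing therefore ensures that selection follows the same grounds in each group.

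Sub-group effects on all pupil outcomes are a stated QED research question. At stake is a difference by sex, ethnicity or FSM that comes from selection and is reported as a treatment effect.

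**Working it through.** **Yardstick.** The point rests on no stated figure, but the QED MDES of 0.20 in SAP Table 8 gives a scale. The SAP 2.2 formula with J = 78 schools (40 and 38), 12 pupils per school, ICC 0.015 and no covariates gives P(1−P)J = 40 × 38 / 78 = 19.49. The variance is 0.015/19.49 + 0.985/(19.49 × 12) = 0.00077 + 0.00421 = 0.00498, with square root 0.0706. The multiplier on 76 df is 1.992 + 0.846 = 2.838, so MDES = 0.200, as stated. For a treatment-by-group difference between two equal halves (6 pupils each, no clustering term), each half has 2.838 × √(1/(19.49 × 6)) = 0.262, and the difference has 0.262 × √2 = 0.37.

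**Check 1: one baseline score, true effect zero.** Assumptions not in the documents: pre-post correlation 0.6, logistic selection with the slopes shown, no clustering, 300 runs. Matching follows the plan: probit score, 1:1, calliper 0.2. About 400 to 430 pairs resulted. The score has main effects only. Gaps are supported minus comparison, in SD.

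| Selection slope, group A / B | Pooled gap | Gap in A | Gap in B | False difference, unadjusted (flagged) | Baseline-adjusted (flagged) |
|---|---|---|---|---|---|
| 0.5 / 0.5 | 0.000 | −0.004 | +0.003 | 0.002 (4%) | −0.003 (5%) |
| 0.35 / 0.65 | −0.001 | −0.126 | +0.096 | 0.128 (13%) | −0.005 (4%) |
| 0.2 / 0.8 | −0.003 | −0.248 | +0.163 | 0.238 (40%) | −0.009 (4%) |

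The false difference is roughly the correlation times the spread of the gaps: 0.6 × (0.126 + 0.096) = 0.13 and 0.6 × (0.248 + 0.163) = 0.25. Inverse weighting left similar gaps (−0.145/+0.123 and −0.305/+0.236). With a group-by-baseline term in the score, and still matching once and then splitting, stratum gaps were at most 0.002 SD and the unadjusted false difference lay between −0.012 and 0.004 SD.

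**Check 2: two baseline scores, true effect zero.** Assumptions: 36 intervention schools, about 410 to 465 supported pupils, 38 × 163 control pupils, ICC 0.015, main-effects probit, 1:1 matching, calliper 0.2, 500 runs. Selection slopes on externalising differ by sex and are mirrored for internalising.

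| Slope, boys / girls | Within-sex externalising gap | SDQ, unadjusted (flagged) | SDQ, baseline-adjusted (flagged) | Suspension-like, own baseline adjusted (flagged) |
|---|---|---|---|---|
| 0.5 / 0.3 | ±0.11 | ±0.06 (13%) | ±0.01 (5%) | ±0.03 (8%) |
| 0.6 / 0.2 | ±0.21 | ±0.11 (34%) | ±0.03 (6%) | ±0.06 (16%) |
| 0.7 / 0.1 | ±0.32 | ±0.16 (62%) | ±0.04 (10%) | ±0.09 (22%) |

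The last three columns are false effects in each stratum, so the boy-girl difference is twice as large: 0.06, 0.12 and 0.18 SD for the suspension-like outcome. The absolute overall imbalance averaged 0.02 to 0.04 SD. Two further runs of this kind gave average pooled gaps of at most 0.003 SD and within-sex gaps of about 0.10 to 0.31 SD. Their suspension-like differences were 0.05 to 0.15 SD (8% to 22% flagged) and about 0.07 to 0.17 SD (11% to 25% flagged).

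Fitting the score and matching within sex brought bias to at most 0.005 SD and flagging to at most about 5%. The loss was about one pair in 438 (437.7 to 436.7, or 0.23%). Exact matching on sex with the pooled main-effects score did not repair the problem. With two baselines, that score weights them wrongly for each sex, so pupils of the same sex with the same score still differ on both.

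**The case against.** A reader might infer that splitting breaks the pairs, so that the stratum comparisons are unmatched. The documents do not support that. Sex, ethnicity and FSM are in the score, and a correctly specified score balances the joint distribution, including within strata. In check 1 with equal slopes, 48% of pairs crossed groups and there was no bias. The planned outcome model is also not a paired analysis.

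A reader might also expect benefit in one group and harm in the other on the primary outcome. The QED model adjusts for baseline, and this took the SDQ error to 0.04 SD per stratum or less. Two limits remain. The sub-group paragraphs do not name that model, and the one sub-group equation in the SAP (2.3.3, for the main trial) has no baseline term. Adjustment for an outcome's own baseline also leaves imbalance in other covariates. SAP 3.4.4 adds relevant demographic and school-level characteristics for secondary outcomes, but does not name the pre-test SDQ scores.

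It would go too far to say that every planned balance check would pass. Mean differences were examined; Rubin's B and R, the Smith-Todd regression test and the Kolmogorov-Smirnov test were not.

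The plan also lists exact matching, CEM and entropy balancing, and places sub-group work after the balancing test and robustness checks. These are alternatives for the overall estimate and are not tied to strata.

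Finally, no passage says that selection differs by sex. That is an assumption, and the slopes are illustrative.

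**Conclusion.** The point holds conditionally. The plan takes sub-group effects from a sample matched and judged only overall, with no group-by-covariate terms named for the score. If selection for support works the same way in each group, there is no bias. If it differs, pooled mean balance can hide stratum gaps of about 0.10 to 0.32 SD under the slopes assumed. That is 10% to 32% standardised bias, against the 2% to 5% that SAP 3.3 calls a good sign.

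For SDQ outcomes the planned baseline adjustment, if carried into the sub-group model, removes most of the error. The exposure is mainly for suspensions, exclusions and attendance, whose own baselines may not capture the imbalance. There the false difference was about 0.05 to 0.18 SD, at most about half of the 0.37 SD detectable (0.18/0.37 = 0.49), flagged in 8% to 25% of null runs against a nominal 5%. Only sex was simulated; the same reasoning applies to ethnicity and FSM. The randomised comparison is unaffected.

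**What to change.** In Protocol Appendix 2 and SAP 3.4.5:

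1. For each of sex, ethnicity (minority/non-minority) and FSM, estimate the propensity score separately within each stratum and match or weight within it. Including group-by-covariate interactions in the score is equivalent. Exact matching on the group variable with the pooled main-effects score is not enough.
2. Report standardised bias and Rubin's B and R within each stratum beside each CATE, and adjust for covariates that remain unbalanced.
3. Estimate the group difference with a treatment-by-group term in the weighted, baseline-adjusted multilevel model, and state that model.

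Stratum balance should be descriptive, not a pass/fail gate. In 100 simulated runs of correctly specified within-stratum matching (8 or 12 covariates, correlation 0.3, about 14 controls per supported pupil), mean standardised bias exceeded 5% in 32% to 37% of runs with 215 supported pupils per stratum and in 69% to 83% with 110. B reached 25 in 5% to 21% and 34% to 79%. A gate would often suppress sound estimates by chance.

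The cost is wording, a few extra model and matching runs, and noisier balance statistics in small strata. Controls are plentiful: with the 6,179 control pupils in SAP Table 6 and 465 supported pupils, the ratio is 6,179/465 = 13.3. The 7,214 in SAP Table 4 would give 15.5.

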STATISTICAL ANALYSIS PLAN

Evaluation of the Trauma Informed Schools UK Training and Implementation (TISUK): A cluster randomised controlled trial

Ipsos UK, The University of Kent, TONIC

Principal investigator: [name], [name],
[name], [name], [name]
[name]

Evaluation of the Trauma Informed Schools UK Training and Implementation (TISUK): A cluster randomised controlled trial

Statistical analysis plan

IPSOS UK, TONIC and the University of Kent

Principal investigators: [name], [name], [name], [name], [name]

Project title	Evaluation of the Trauma Informed Schools UK Training and Implementation (TISUK): A cluster randomised controlled trial
Developer (Institution)	TISUK
Evaluator (Institution)	Ipsos UK, The University of Kent, TONIC
Principal investigator(s)	[name], [name], [name], [name], [name]
SAP author(s)	[name], [name]
Trial design	Two-armed cluster randomised controlled trial with random allocation at the school level
Trial type	Efficacy
Evaluation setting	School
Target group	Children and young people (CYP) in Year 8
Number of participants	100 schools and 16,000 Year 8 pupils (with 1,100 receiving targeted support)

Primary outcome and data source
	
Externalising behaviour: SDQ – combined conduct and hyperactivity scores (Survey)


Secondary outcome and data source
	
(CYP) Internalising behaviour: SDQ – combined emotional regulation and peer problems (Survey)
 
(CYP) Prosocial behaviour: SDQ – Prosocial behaviour (Survey)
 
(CYP) Total difficulties: SDQ – combined emotional regulation, hyperactivity, conduct, and peer problems (Survey)
 
(CYP) Non-psychotic psychological distress: General Health Questionnaire (GHQ12) (Survey)
 
(CYP) Well-being: Short Warwick Edinburgh Mental Well-being Scale (Survey)
 
(CYP) Sense of connectedness: School Connectedness Scale (Survey)
 
(CYP) Percentage of exclusions & suspensions: administrative records
 
(CYP) School attendance: administrative records
 
(School staff) Attitudes related to TIC: Attitudes Related to Trauma Informed Care (ARTIC) (Survey)
 
(School staff) Well-being: Short Warwick Edinburgh Mental Well-being Scale (Survey)
 
(School) Staff retention: administrative records
 
(School) Staff sickness: administrative records
 
(School) Percentage of exclusions & suspensions of CYP: administrative records
 
(School) Percentage of school attendance of CYP: administrative records

Version	Date	Changes made and reason for revision
1.1	July 2024	Updated section on compliance (see section 2.3.9)
1.0 [original]	April 2024	[leave blank for the original version]

Any changes to the design or methods need to be discussed with the YEF Evaluation Manager and the developer team prior to any change(s) being finalised. Describe in the table above any agreed changes made to the evaluation design. Please ensure that these changes are also reflected in the SAP (CONSORT 3b, 6b).

Table of contents

1	Introduction.....	6
2	Main trial on whole school intervention	7
2.1	Design overview	7
2.2	Sample size calculations overview	11
2.3	Analysis.....	16
2.3.1	Primary outcome analysis	20
2.3.2	Secondary outcome analysis	22
2.3.3	Sub-group analysis	22
2.3.4	Further analysis	24
2.3.5	Interim analyses and stopping rules	24
2.3.6	Longitudinal follow-up analyses	24
2.3.7	Imbalance at baseline	25
2.3.8	Missing data	26
2.3.9	Compliance	27
2.3.10	Intra-cluster correlations (ICCs)	28
2.3.11	Presentation of outcomes	29
3	Embedded QED study on targeted intervention	29
3.1	Design overview	29
3.2	Sample size calculations.....	30
3.3	Selection of the comparison group and identification assumptions	32
3.4	Analysis.....	34
3.4.1	Primary analysis	35
3.4.2	Inference	36

3.4.3	Robustness Checks	36
3.4.4	Secondary analyses	36
3.4.5	Subgroup analyses	37
3.4.6	Further analyses	37
3.4.7	Treatment effects in the presence of non-compliance	37
3.4.8	Missing data	38
3.4.9	Presentation of outcomes	38
4	References	38

1 Introduction

The intervention is called Trauma Informed Schools UK Training and Implementation. It is a whole-school intervention aimed at improving school staff awareness of trauma-informed practices (TIPs) and implementing changes in policies and practices consistent with TIPs.

The intervention targets school staff, who are expected to implement institutional changes, and all children and young people (CYP) attending the school. The intervention encompasses various activities:

1. Whole staff training: Two 3-hour sessions for all staff, including support staff and administrators, providing an overview of trauma, its impact, adverse childhood experiences (ACEs), protective factors, neuroscience of trauma, and relational approaches.
2. Senior leadership training: A 2-day training session for 5-7 members of the Senior Leadership Team (SLT) from each school, focusing on creating a trauma-informed and mentally healthy culture through ethos, policy, and practice.
3. Network consultancy support: Three consultancy support meetings for school leaders to embed changes in culture, policy, and practice and identify and overcome implementation barriers.
4. Diploma practitioner training: An 11-day Level 5 Diploma Practitioner Training for 5-7 staff members from each school, providing a deeper understanding of trauma and its recovery process and equipping them with skills and knowledge to respond effectively and support the most vulnerable pupils through individual or small group support.
5. Reflective supervision workshops: Training for two practitioners from each school to establish an effective, sustainable reflective supervision model for key staff.
6. Webinar viewing for staff and CYP: Access to webinars on topics related to trauma, relationships, emotions, and gangs/violence, with discussions facilitated by teachers.

The expected outcomes within the first 5-6 months include increased knowledge, understanding, and skills among staff; enhanced staff support structures and changes in school policies and procedures; improved mental health and well-being, reduced exclusions, and increased engagement among students.'

Further information on the intervention can be accessed here: <https://www.traumainformedschools.co.uk>

This programme will be evaluated through an efficacy trial, a two-arm and a cluster-randomised controlled trial (cRCT). The trial is clustered at the school level as the programme is a whole-school intervention. Every school that signs up to participate in the trial will have an equal probability (50%) of being assigned to the treatment or control groups. In addition, the trial is complemented by an Implementation and Process Evaluation (IPE) and an embedded quasi-experimental design (QED).

The main focus of the process evaluation will be to accurately assess the extent to which the intervention is implemented as intended throughout the school, ensuring fidelity to the intervention's principles. In addition to fidelity, other dimensions to test are dosage, responsiveness, quality, and reach.

The intervention comprises two participation levels for children and young people (CYP). At the whole school level, staff implement structural changes affecting all CYP, with outcomes measured in Year 8. At a targeted level, diploma practitioners provide tailored support to a subgroup of CYP with trauma history. A Study Within a Trial (SWAT) focuses on Year 8 CYP for additional support, employing a quasi-experimental design with propensity score matching (PSM) due to non-randomised control group selection (covered in section 3 below).

2 Main trial on whole school intervention

